6.2.3 On-Study Evaluations

After counseling, laboratory testing and randomization, participants will receive sufficient TDF/FTC study medication to last until the next scheduled visit (either 4 or 12 weeks) through the investigational pharmacy. Medication renewals will not be available if a subject misses a scheduled appointment. An informational pamphlet on TDF/FTC will be provided that will summarize the label package insert information for patients (in English or Spanish) with changes made to tailor the information for someone that is not HIV infected. Participants will be directed to take one pill once a day at a convenient routine time. If there are missed doses, participants will be told to take the next scheduled dose on time and not to take any additional pills to catch up. Bottles with any remaining missed doses will be returned to the pharmacy at the time of medication renewal and the number of untaken doses will be recorded. At each clinic visit, TDF/FTC medication adherence will be

reviewed by the clinician, adverse events will be queried and adherence and barriers to adherence will be discussed. All subjects will receive episodic adherence counseling within the confines of routine clinic visit. Each clinic visit will also include blood draw for calculated GFR (serum creatinine) and plasma FTC drug levels, and HIV testing. STI testing including NAT screening for GC and chlamydia from throat and rectal swabs and from urine and RPR from blood will be done at week 0 and every 24 weeks thereafter.

Adherence and Behavioral Assessments

We will measure adherence using the ACTG medication adherence questionnaire [25]. At each follow-up visit, the ACTG four-day questionnaire will be administered using the web-based data capture system. The instrument tracks the number of doses skipped over the past four days and reasons why medications may have been skipped. In addition, we will ask their ability to adhere by Likert scale and use the Visual Analog Scale (VAS), which appears as an ordinal scale representing the percent of medication taken relative to that which has been prescribed over the past 4 weeks. Subjects are presented with a line anchored at 0% and 100% and are asked to mark a line on the scale indicating their own PrEP adherence [26].

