- Some people get busy and forget to take their pills with them.

- Some people find it hard to take their pills according to all the instructions, such as “with food”, “on an empty stomach”, “every 8 hours”, or “with plenty of fluids”.
- Some people choose to skip pills to avoid side effects or to just not be taking pills that day.

We need to understand how people on PrEP are really doing with their pills. Please tell us what you are actually doing. Don't worry about telling us that you don't take all your pills. We need to know what is really happening, not what you think we “want to hear.”

Complete frequency of drug

1. **How many times a day are supposed to take your PrEP medication?** _____

2. **How many pills you supposed to take when you take this drug?** _____

3. **Are you currently taking any of your PrEP medication?**

No.....0
 Yes.....SKIP TO QUESTION 6.....1

4. **Why are you not taking your PrEP medication? (CIRCLE ALL THAT APPLY)**

I wanted to avoid the side effects.....1
 Not having sex.....2
 Having sex but do not think you are at risk.....3
 Don't believe in these medications.....4

5. **Over the last 4 days, have you not been able to take any of your PrEP medication?**

No.....SKIP TO QUESTION 7.....0
 Yes.....1

6. **The next section of the questionnaire asks about the PrEP medication that you have not been able take taking over the last four days. When were not able to take your medication (check all that apply)**

Yesterday.....1
 Day before yesterday ((2 days ago).....2
 3 days ago.....3
 4 days ago.....4

7. **PrEP medication would best be taken at the same time every day. How closely did you take the medication at about the same time over the last four days?**

Never.....0
 Some of the Time.....1
 About Half of the Time.....2
 Most of the Time.....3
 All of the Time.....4

8. Some people find that they forget to take their pills on the weekend days. Were you not able to take any of your PrEP medication last weekend—last Saturday and Sunday?

No.....0
 Yes.....1

9. Including the four days you just described, when was the last time you were not able to take your PrEP medication?

Never missed PrEP medication.....0
 More than 3 Months Ago.....1
 1—3 Months Ago.....2
 2—4 Months Ago.....3
 1—2 Weeks Ago.....4
 Within the Past Week.....5

Instructions: For participant to complete questions 12 and 13.

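### As printed, the 4-day adherence form sends current PrEP takers past its direct yes/no question on missed days, so at question 6 full adherence and non-response leave the same blank

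*Combined protocol and SAP*

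**What the plan says.** The primary endpoint (Schema, Outcomes; Section 9.1) adds up self-reported days from five ACTG questionnaires, at weeks 4, 12, 24, 36 and 48, and requires at least 18 of 20. Section 9.1 counts a missing form as zero doses. Section 6.2.3 describes the form by what it counts: "The instrument tracks the number of doses skipped over the past four days". It also gives the mode: "the ACTG four-day questionnaire will be administered using the web-based data capture system".

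The form is printed in Appendix II under PrEP Adherence:

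- Question 3 (currently taking PrEP?) has the response line "Yes.....SKIP TO QUESTION 6.....1".
- Question 4 asks those not taking it why not.
- Question 5 asks "Over the last 4 days, have you not been able to take any of your PrEP medication", with the response line "No.....SKIP TO QUESTION 7.....0".
- Question 6 is a check-all list of four days, from yesterday to four days ago. It has no code for none.
- Question 9 asks when a dose was last missed. Code 0 means never, codes 1 to 4 place the last miss a week or more ago, and the last code is "Within the Past Week.....5".

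The 4-week recall section of the same appendix has a separate seven-day pill item (its question 5).

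**The concern.** Question 6 presupposes a miss, so it works only after question 5 has screened for one. As printed, that screen reaches only people who say they are not taking PrEP. A current taker with a perfect four days has nothing to tick at question 6, and a current taker who skips the item also ticks nothing.

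Question 6 is the item that says which days were missed, so it feeds the 18-of-20 count. The plan gives no rule for a blank item on a submitted form. Scoring the blank as 4 of 4 credits non-response as full adherence. Scoring it as missing penalises people who took every dose. Either way, one unanswered item can decide a subject's primary outcome.

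**Working it through.** **1. Routing.** Question 3 = yes leads to question 6, so questions 4 and 5 are not seen. Question 3 = no leads to questions 4 and 5, and question 5 = no then leads to question 7. The direct no-misses answer (question 5 = no) is therefore reachable only after question 3 = no.

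**2. Endpoint arithmetic.** 5 forms × 4 days = 20 days, and 18/20 = 90%, which reproduces the stated threshold. For an otherwise perfect subject with one blank:

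- blank scored 4/4: 16 + 4 = 20 of 20, a pass;
- blank scored 0/4: 16 + 0 = 16 of 20 = 80%, a fail.

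**3. The plan's power.** Section 9.4 gives 200 per arm, two-sided alpha 0.05, and 30% (standard of care) against 15% (intervention). I read these as failure rates, because the intervention arm has the lower one. Full enumeration of the two-sided Fisher test gives 94.0% for 30% v 15% and 84.5% for 30% v 17%, against 94% and 84% stated.

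**4. How often a blank can turn a fail into a pass, if blank = 4/4.** Failing on adherence needs at least 3 missed days. A blank helps only if it falls on a form carrying misses and leaves 2 or fewer. Over every pattern of 0 to 4 missed days on each of five forms, the easiest to rescue is one miss on each of three forms. With blank probability q per form, the chance of rescue is then at most 1 − (1−q)³.

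**5. Upper bound on the effect.** The documents give no item non-response rate, so q is assumed, equal by arm and independent of adherence and visit. With k = (1−q)³, the failure rates become 0.30k and 0.15k, the difference 15k points, and the number misclassified 200 × 0.45 × (1−k).

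| q | k | Misclassified of 400 | Failure rates | Difference (points) | Fisher power |
|---|---|---|---|---|---|
| 0 | 1 | 0 | 30.0% v 15.0% | 15.0 | 94.0% |
| 1% | 0.970 | 2.7 | 29.1% v 14.6% | 14.6 | 93.1% |
| 2% | 0.941 | 5.3 | 28.2% v 14.1% | 14.1 | 92.1% |
| 5% | 0.857 | 12.8 | 25.7% v 12.9% | 12.9 | 88.7% |

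**6. Milder case.** Failures from stopping PrEP or missing a visit cannot be rescued by a blank. If half of failures are of that kind (assumed), k is replaced by 0.5 + 0.5k.

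| q | Misclassified, at most | Difference (points) | Fisher power |
|---|---|---|---|
| 1% | 1.3 | 14.8 | 93.6% |
| 2% | 2.6 | 14.6 | 93.1% |
| 5% | 6.4 | 13.9 | 91.7% |

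**The case against.** The strongest objection is that the blank is often resolvable. Current takers still reach question 9, where codes 0 to 4 imply no miss in the past week. A reader might infer that question 5 = no is the form's only way to record full adherence; question 9 shows that it is not. There is other information too. The schedule of evaluations has an adherence review at each follow-up visit, Section 6.2.3 has the clinician review adherence and the pharmacy record returned doses, and Section 6.3.12 records the date and time of the last three doses. All of this stands, and it lowers the priority. None of it is a scoring rule, however, and the plan does not say that any of it is used to read a blank question 6.

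The second objection is that only a print is visible. The survey is run on the web and its programmed routing is not shown. The print has another numbering oddity: the instruction "For participant to complete questions 12 and 13" stands before question 10, so the skip target may be a slip of the same kind. This also stands. The documents do not support saying that participants were misrouted, only that the printed form would misroute them.

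Third, Section 9.0 leaves detail to a SAP to be finalised before database lock. That is where the scoring rule belongs, but a wrong skip target is not something a SAP can correct for visits still to come.

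**Conclusion.** The point holds for the form as printed: at question 6, full adherence and item non-response cannot be told apart, and no stated rule separates them. It is minor. Under blank = 4/4, the loss at assumed blank rates of 1%, 2% or 5% is at most 2.7, 5.3 or 12.8 subjects and 0.9, 1.9 or 5.3 points of power (94.0 less 93.1, 92.1 and 88.7). These are ceilings, since they give every failing subject the most rescuable pattern.

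Two stronger readings are tempting, and neither is supported. One is that any blank on any of the five forms rescues any failing subject; the 18-of-20 rule makes that impossible for every pattern of misses. The other is that the flaw necessarily pulls the arms together. That holds only if a blank is scored 4/4 and blank rates are equal by arm. If a blank is scored as missing, the error runs the other way, against adherent subjects. The figures do not cover blank rates that differ by arm.

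**What to change.** First check the live routing. If it matches the print, send question 3 = yes to question 5, or add a none-missed code to question 6, for the remaining visits, and flag the form version.

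For forms already completed, state in the SAP before database lock how a current taker's blank question 6 is scored, using the content of the other answers and not merely whether they were answered:

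- **4/4** if question 9 is coded 0 to 4 and the seven-day pill item does not contradict it.
- **0/4**, in line with Section 9.1, if questions 7 to 9 and the seven-day item are all blank, or if the seven-day item reports no pills taken.
- **All others:** bound the result by scoring them 4/4 and then 0/4. Question 9 = within the past week belongs here, because it also covers misses 5 to 7 days ago, outside the four-day window.

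Report the number of such forms by arm.

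The cost is one skip target or response code, a version flag, a short scoring rule and one extra analysis. The drawback is two form versions in the data. Section 6.5.2 indicates that some subjects have already had their final visit; for their forms only the scoring rule helps.

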CCTG 595 Vitamin D Sub-study

Effect of Vitamin D Supplementation on Bone Turnover Markers during Tenofovir-Emtricitibine Pre-Exposure Prophylaxis in Men Who have Sex with Men

DESIGN	
CCTG 595 is an open-label clinical trial of the effect of text messaging intervention vs. standard of care on adherence to Truvada (tenofovir-emtricitibine) as PrEP in MSM at increased risk of HIV infection.
 
This sub-study is a matched case-control study, in which cases prospectively take vitamin D3 4000 IU/day beginning at week 24 of PrEP.

DURATION	
Subjects will be followed for 6 months (24 weeks)

SAMPLE SIZE	
50 eligible subjects will receive vitamin D and will be compared to 50 matched control subjects from CCTG 595 who are not participating in this sub-study.

POPULATION	
HIV-negative men aged ≥ 18 years initiating CCTG 595, who are not taking bisphosphonates and do not have a history of osteoporosis, fragility fracture, or kidney stones, or use of tenofovir prior to entry into CCTG 595

REGIMEN	
Vitamin D3 4000 IU/day from week 24 through 48 of PrEP with Truvada

ENDPOINTS	
Primary endpoint will be changes in bone turnover markers from week 24 through week 48 in the vitamin D intervention group as compared to age- and BMI-matched controls

ANALYSIS	
A sample size of 44 subjects per group will provide 80% power to detect a 20% change in P1NP means from week 24 through week 48 between matched cases and controls using a paired t-test with a two-sided $\alpha = 0.05$. To account for attrition, a sample size of 100 is proposed, including 50 vitamin D treated cases and 50 matched controls from CCTG 595.

1.0 HYPOTHESIS AND STUDY OBJECTIVES

1.1 *Hypothesis*

Supplementation with vitamin D 4000 IU/day will significantly blunt the increases in BTMs that occur after initiation of PrEP with Truvada.

1.2 *Primary Objective*

To compare the change in P1NP levels from week 24 through week 48 among subjects (cases) who receive vitamin D 4000 IU/day to the change in levels seen in matched unsupplemented controls.

1.3 *Secondary Objectives*

1.3.1 To compare the change in CTX levels from week 24 through week 48 among subjects who receive vitamin D 4000 IU/day to the change in levels seen in matched unsupplemented controls.

1.3.2 To compare the change in PTH level from week 24 through week 48 among subjects who receive vitamin D 4000 IU/day to the change in levels seen in matched unsupplemented controls.

1.3.3 To compare vitamin D levels at week 48 among subjects who receive vitamin D 4000 IU/day and matched unsupplemented controls.

1.3.4 To demonstrate the change in P1NP, CTX, PTH, and vitamin D levels from baseline to week 24 in both cases and controls.

2.0 INTRODUCTION

2.1 *Background and Rationale*

Current HIV treatment guidelines recommend combination antiretroviral therapy with three active ARVs and 7 of the 9 currently recommended initial combination regimens for ART-naïve patients include tenofovir disoproxil fumarate (TDF) ¹. While treatment with TDF-containing antiretroviral treatment (ART) regimens have proven durable, tolerable, and effective, TDF has well described toxicities, including greater loss of bone mineral density (BMD) in the first 48 weeks after ART initiation and an increased risk for fragility fracture ²⁻⁴. The FDA recently approved TDF given with emtricitabine (FTC) as a single daily fixed dose combination (FDC) pill (Truvada (TDF/FTC)) for Pre-Exposure Prophylaxis (PrEP) to prevent HIV acquisition for persons with increased risk for HIV infection. In studies evaluating the efficacy of TDF/FTC for PrEP, daily use has been shown to significantly reduce BMD ^{5,6} albeit to a lesser extent than that seen during initial treatment for HIV. Although TDF-containing PrEP has not yet been associated with increased fracture risk, reduced BMD is nonetheless a concern for patients and providers of PrEP. Thus, strategies are needed to attenuate or prevent BMD loss, particularly when TDF-containing PrEP will be given for prolonged periods of time. The mechanism by which TDF induces BMD loss is unclear but appears to be mediated

through a reduction in PTH levels and PTH-controlled calcium and phosphate metabolism⁷. Additional data from ATN 063 suggest that TDF induces a state of functional vitamin D deficiency⁸

Recently, Overton and colleagues reported a dramatic reduction in the magnitude of BMD loss during initial therapy of HIV infection with vitamin D (4000 IU/day) and calcium supplementation⁹ when co-administered with efavirenz/TDF/FTC ART. The amount of BMD loss at the hip measured by DXA over 48 weeks with vitamin D-calcium was approximately half that seen with placebo (-1.5% vs. -3.2%, respectively, $p < 0.001$), and was reduced to levels that would be expected with ART that does not contain TDF. Notably, the median daily vitamin D intake was low for the cohort (120 IU/day) while calcium intake approached recommended daily intake (810mg). Thus, these data provide a strong rationale to study prophylactic administration of daily oral supplemental vitamin D in subjects receiving PrEP with Truvada.

In ACTG 5280, vitamin D-calcium supplementation prevented the increase in parathyroid hormone (PTH) and blunted the increase in bone turnover markers (BTMs), including P1NP (a marker of bone formation) and CTX (a marker of bone resorption). Importantly, there was a good correlation between changes in DXA-measured BMD over time and changes in BTMs, particularly with P1NP. The percentage change of P1NP at week 48 correlated with the percentage change in total hip BMD ($r = -0.32$, $p = 0.01$) as well as the change in lumbar spine BMD ($r = -0.37$, $p = 0.002$) [Overton ET, unpublished data]. Due to the difficulties and expense of performing DXA scans in a clinical trial, P1NP levels are proposed as the primary outcome measure for this pilot trial.

CCTG 595 is an open-label clinical trial of the effect of a text messaging intervention vs. standard of care on adherence to Truvada as PrEP in MSM at increased risk for HIV infection (ClinicalTrials.gov Identifier: NCT01761643). Approximately 1/3 of the planned 400 subjects have been enrolled as of April 2014. Study sites include University of California at San Diego, University of Southern California, and Harbor-UCLA Medical Center.

Rationale for use of vitamin D dose: The dose of vitamin D (4000 IU/day) in this protocol carries little risk for the study subjects. This dose was without adverse effects in a more ill population, namely the HIV-infected subjects in ACTG 5280 (see above). Generally, vitamin D supplementation is well tolerated and safe. Dosages up to 10,000 IU daily in healthy adults is considered safe and the current upper U.S. Dietary Reference Intake of 2,000 IU daily is considered to be well below the actual physiologic requirements^{10,11}. The Institutes of Medicine guideline considers 4000 IU/day to be the safe upper limits for daily intake for adults <http://www.iom.edu/Reports/2010/dietary-reference-intakes-for-calcium-and-vitamin-D/DRI-values.aspx>. Several studies have focused specifically on the safety of chronic daily administration of 4000 IU¹²⁻¹⁴. In these studies, 228 adult subjects received 4000 IU/day vitamin D with excellent tolerability, no toxicity, and a concomitant increase in 25 (OH) vitamin D levels ranging from 39-51 ng/mL. No abnormalities in serum calcium or urinary calcium excretion were noted.

In this study supplemental calcium will not be used because: a) in ACTG 5280, calcium intake among untreated HIV-infected subjects was generally adequate⁹. It can be anticipated that the largely healthy HIV-uninfected subjects in CCTG 595 will have levels of intake that are higher than the diseased population in ACTG 5280. This suggests supplemental calcium will not be required for 4000 IU/d vitamin D's beneficial effects,

particularly in the CCTG 595 subjects; b) there is concern that multiple additional pills a day may influence adherence with the primary intervention used in CCTG 595.

3.0 STUDY DESIGN

CCTG 595 is an open-label clinical trial of the effect of a text messaging intervention vs. standard of care on adherence to Truvada as PrEP in MSM at increased risk for HIV infection (ClinicalTrials.gov Identifier: NCT01761643). Eligible subjects for this matched case control substudy will receive vitamin D 4000 IU/day for 24 weeks, from week 24 through week 48. In CCTG 595, plasma from participants are being collected and stored at entry and every 12 weeks. These plasma samples will be used to measure P1NP, CTX, PTH, and vitamin D levels in both cases and controls at entry, week 24, and week 48.

4.0 SELECTION AND ENROLLMENT OF SUBJECTS

4.1 *Inclusion Criteria*

4.1.1 All subjects must meet CCTG 595 inclusion criteria.

4.2 *Exclusion Criteria*

4.2.1 All subjects must meet CCTG 595 exclusion criteria.

4.2.2 Current or prior use of bisphosphonate therapy.

4.2.3 Current use of vitamin D supplements greater than 400 IU/day.

4.2.4 Current use of androgenic hormones or growth hormones.

4.2.5 History of nephrolithiasis (kidney stones).

4.2.6 History of fragility fracture.

4.2.7 No use of tenofovir prior to entry into CCTG 595

4.3 *Study Enrollment Procedures*

Once a candidate for study entry has been identified, details will be carefully discussed with the subject. The subject will be asked to read and sign the approved protocol consent form. Participation in this substudy is not required for continued participation in CCTG 595.

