4.2 Main Study Exclusion Criteria

- 4.2.1 Unable to give informed consent.
- 4.2.2 Active hepatitis B (positive hepatitis B surface antigen (HBSAg) or HBSAg negative/ HB core antibody positive/ HBV PCR positive)
- 4.2.3 Has substantial medical condition, that in the opinion of the investigator would preclude participation, as defined by
- ◆ cardiovascular condition that may lead to an increased risk of complication if placed on study drugs.
 - ◆ gastrointestinal condition that would impair absorption of study drugs.
 - ◆ neurological or psychiatric condition that would significantly impair the ability to adhere to PrEP.
 - ◆ calculated GFR < 60 mL/min
 - ◆ alcohol or drug abuse or dependence that would significantly impair the ability to adhere to PrEP (only for those with severe impairment).
 - ◆ Other medical condition that would unacceptably increase the risk of harm from study drug or significantly impair the ability to adhere to PrEP.
- 4.2.4 Suspected sensitivity or allergy to the study drug or any of its components.
- 4.2.5 Currently using an essential product or medication that interacts with the study drug such as the following:
- ◆ ART (including nucleoside analogs, non-nucleoside reverse transcriptase inhibitors, protease inhibitors or investigational antiretroviral agents)
 - ◆ Agents with known nephrotoxic potential:
 - aminoglycoside antibiotics (including gentamicin)
 - IV amphotericin B
 - cidofovir
 - cisplatin
 - foscarnet
 - IV pentamidine
 - IV vancomycin

- oral or IV gancyclovir
- other agents with significant nephrotoxic potential
- ◆ Drugs that slow renal excretion
 - Probenecid
- ◆ Immune system modulators
 - Systemic chemotherapeutic agents (i.e. cancer treatment medications)
 - Ongoing systemic corticosteroids (with the exception of short courses of tapering steroid doses for asthma or other self-limited condition).
 - Interleukin-2 (IL-2)
 - Interferon (alpha, beta, or gamma)
- ◆ Other agent known to have a significant interaction with TDF or FTC

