5.4.1.1 All investigational drugs

5.4.1.2 All HIV vaccines

5.4.1.3 Any immunomodulators

5.4.1.4 Systemic cytotoxic chemotherapy

5.4.1.5 All other antiretroviral medications (excluding FTC/TDF given as PEP or PrEP)

5.4.1.6 Drugs with known nephrotoxicity

Subjects must have discontinued prohibited medications at least 30 days prior to entry.

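### Vitamin D sub-study exclusion 4.2.7 on prior tenofovir has the opposite polarity to the synopsis, osteoporosis is missing from the exclusion list, and the list is not stated to apply to matched controls

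*Combined protocol and SAP*

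**What the plan says.** Section 4.2 of the vitamin D sub-study is headed as an exclusion list. Items 4.2.2 to 4.2.6 each name something whose presence disqualifies, for example "Current or prior use of bisphosphonate therapy" (4.2.2) and "History of fragility fracture" (4.2.6). The last item, 4.2.7, reads "No use of tenofovir prior to entry into CCTG 595".

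The Population row of the sub-study synopsis describes HIV-negative men who are not taking bisphosphonates and who "do not have a history of osteoporosis, fragility fracture, or kidney stones, or use of tenofovir prior to entry into CCTG 595".

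Sub-study item 4.2.1 brings in the main-study criteria by reference: "All subjects must meet CCTG 595 exclusion criteria". On antiretrovirals, main-study exclusion 4.2.5 concerns someone "Currently using an essential product or medication that interacts with the study drug such as the following". The main-study list of prohibited medications, item 5.4.1.5, exempts TDF/FTC taken as post- or pre-exposure prophylaxis.

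Controls are defined in the Matching paragraph of sub-study section 9.2. They are concurrent CCTG 595 subjects outside the sub-study who report no more than 400 IU of vitamin D a day. They are matched 1:1 on main-study arm, age, race/ethnicity, season of entry and BMI.

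**The concern.** The eligibility list is what screening forms and monitoring visits would follow. If its tenofovir item says the reverse of the population statement, a site cannot comply with both, and either choice is a deviation from one of them. Someone working from list 4.2 alone would not learn that osteoporosis is meant to exclude.

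The sub-study measures bone turnover markers during TDF/FTC, so earlier tenofovir exposure and existing bone disease are factors one would want handled alike in both groups. The design is not randomised. Comparability rests on the matching factors and on shared eligibility, and shared eligibility is not written down.

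**Working it through.** No sample size or power figure is in dispute. The check is a comparison of the four places that define who may take part.

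| Factor | Synopsis, Population | Sub-study list 4.2 | Main-study criteria | Stated for controls (9.2)? |
|---|---|---|---|---|
| Prior tenofovir | must be absent | 4.2.7: absence excludes | current antiretroviral use only | no |
| Osteoporosis | must be absent | not named | not named | no |
| Fragility fracture | must be absent | excludes | not named | no |
| Kidney stones | must be absent | excludes | not named | no |
| Bisphosphonates | not currently taking | current or prior use excludes | not named | no |
| Vitamin D above 400 IU/day | not mentioned | excludes | not named | yes |
| Androgenic or growth hormones | not mentioned | excludes | not named | no |

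**Tenofovir.** A man with no earlier tenofovir meets the synopsis and fails 4.2.7 as worded. A man with earlier tenofovir passes 4.2.7 and fails the synopsis. Every candidate is one or the other, so the two texts together admit nobody. The main study does not settle the matter: it excludes current antiretroviral use and exempts prophylactic TDF/FTC from the prohibited list, so former users can properly be enrolled in CCTG 595.

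**Osteoporosis.** It appears in the synopsis only. The fragility-fracture and bisphosphonate items catch part of that group, but osteoporosis can be present without a fracture or that treatment.

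**Controls.** The sub-study uses eligibility language for those who take vitamin D. Section 3.0 says the eligible subjects receive it, and section 6.0 speaks of subjects and controls separately. Of the seven factors above, section 9.2 states one for controls.

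**Which comparison is exposed.** Objective 1.3.4 uses the change from baseline to week 24. For a former user, the entry sample is not a level from before any tenofovir. The primary endpoint is the P1NP change from week 24 to week 48, by which time every subject has been prescribed about 24 weeks of TDF/FTC. Pre-entry exposure therefore bears less directly on it.

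**Rough size, by assumption.** The documents give no rate of earlier tenofovir use in CCTG 595. The nearest figure, in main-protocol section 2.1, is 4% using PrEP in initial studies of MSM. It measures current rather than past use, so it is only a marker.

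- At 4%: 0.04 × 50 = 2 of 50 cases, and likewise 2 of 50 controls.
- Each further percentage point adds 0.01 × 50 = 0.5 of a subject per group.
- Suppose former users' P1NP change differed from that of naive men by as much as the whole planned 20% difference, and all of them fell in one group. That group's mean would move by 0.04 × 20 = 0.8 percentage points. If they were spread evenly and responded alike in both groups, the shift would cancel in the comparison.

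**The case against.** The best defence is that nobody would apply 4.2.7 literally. Item 4.2.1 in the same list is also phrased as a requirement, and read literally it would be just as inverted, yet its meaning is obvious. Read as a requirement, 4.2.7 agrees with the synopsis. A rule that barred every tenofovir-naive man would halt recruitment at once and be noticed. This stands. A reader might infer that the whole intended pool for the 50 cases and 50 controls would be lost, but the documents do not support that as a forecast, and for controls they do not say that 4.2.7 applies at all.

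It can also be said that the synopsis is an abbreviation (it leaves out the vitamin D and hormone exclusions), that the fracture and bisphosphonate items cover much of the bone-disease group, and that main-study 4.2.8 lets an investigator exclude anyone whose condition would cloud the outcome data. This stands in part. The osteoporosis point is a mismatch with partial cover rather than a flat contradiction. But abbreviation explains items missing from a synopsis, not an item missing from the detailed list, and a discretionary clause does not secure uniform handling across sites.

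Finally, the background section calls this a pilot, and section 9.1 says that P1NP data under TDF without HIV infection are not available. This is a fair limit on any claim of bias.

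**Conclusion.** The wording error in 4.2.7 is plain on the page, as is the absence of osteoporosis from list 4.2. The main-study criteria repair neither. The more substantive gap is that most of the 4.2 exclusions are not stated for controls, while matching covers arm, age, race/ethnicity, season and BMI but not earlier tenofovir, osteoporosis, fracture or bisphosphonate use.

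The likely size is modest: a few misclassified subjects, on the order of 2 per 50 if the 4% marker is anywhere near right, with objective 1.3.4 the most exposed.

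Two stronger inferences should be resisted. One is that cases and controls are both selected by the faulty list; section 9.2 does not say so. The other is that earlier exposure is known to alter the week 24 to 48 P1NP change; the documents contain no data on this, so bias is possible and not shown. The main trial's endpoint, power and analysis are untouched.

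This rests on the synopsis expressing the intended population for tenofovir, which the sub-study's hypothesis about marker increases after starting PrEP supports.

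**What to change.** 1. Reword 4.2.7 so that it names the disqualifying fact, with the same polarity as the synopsis: use of tenofovir before entry into CCTG 595. The requirement-style phrasing of 4.2.1 can be tidied at the same time.
2. Reconcile the synopsis and list 4.2 on osteoporosis and on bisphosphonates (current use against current or prior use), so that both state the same rule.
3. State in the Matching paragraph of section 9.2 that controls must meet the same eligibility list as cases.
4. If subjects have already been enrolled or matched, check them against the reconciled list and report how many do not meet it.

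The cost is a few lines of text and a somewhat smaller pool of eligible controls. One practical point follows from step 3: main-study section 6.3.3 records only medications taken in the 30 days before entry. Earlier tenofovir or bisphosphonate use in controls may therefore need a short added history question, or should be reported as unknown.
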